## **2. Organizational Participation of the Stakeholders**

The patients and other stakeholder groups are tightly interwoven into the study governance. They represent 8 out of 9 groups (8 out of 13 individuals) on the Executive Committee that meets monthly to monitor and govern the study. In addition, each of the stakeholder groups has a specific co-Investigator liaison on the Operations Committee (OC) (responsible for supervising operations). These liaisons are responsible for managing interactions with each stakeholder group. Due to the importance of the patient voice in this research, we are employing [name], an AA/Hispanic asthma educator as a specific manager of these interactions assisted by [name], an expert in community outreach. A Spanish interpreter ([name]) has been provided, if desired by any H/L stakeholder. [name] will be a member of the Executive Committee as well as the Operations Committee. All stakeholders will be invited and reimbursed for attending the 2 day study start-up meeting to engage all participants and to hear patient voices. In addition, there will be a 2-day meeting in year 5 for the whole team to work on analysis, interpretation and development of understandable messages. Before and between the in-person meetings, the groups will meet regularly by conference call and webinar to assure they are fully engaged in following the study progress and dealing with problems that arise in the conduct of any study. Further, we are not only incorporating the voice our patient stakeholders in our study, we are actually incorporating actual patient subject voice into designing our study as described in our Vanguard study process. During the final 2 years, our stakeholders will spend considerable time helping us develop the dissemination goals and strategies that they have already begun to consider. All partners and stakeholders are compensated for their time and attendance at equal rates. Patient input will be channeled through two different mechanisms throughout this trial. [name] [name], a native of Puerto Rico, and [name], an African-American educator, will be the Operations Committee representatives to the H/L and AA patients. With the assistance of our patient facilitators, they will meet regularly and on an ad hoc basis (frequency will depend on the phase of the study with their respective groups to seek their feedback and communicate their input for the Operations Committee. Additionally, the groups will have direct representation on the Executive Committee of the study. [name], [name], and [name] will respectively represent the AA, H/L, and patient advocacy committees to the Executive Committee. The Executive Committee sets the policy for the entire study, approves all protocols, approves all budgets and extraordinary expenditures, established new committees, and reviews all publications and communications. Additionally, all committees and subcommittees to be established will either include representatives of the patient stakeholder committees, e.g., dissemination, or include specific liaisons who will be responsible for meeting with, and channeling, stakeholder input.

## **G. Project Milestones and Timeline**

Work in the first nine months will focus on obtaining initial IRB approvals, developing training materials, and preparing the data collection systems, the patient contact systems, and reminder systems for surveys.

From Q3 of Year 1 – 1st month of Year 2, we will enroll the Vanguard cohort, extensively evaluate and work with our stakeholders to interpret the data from the Vanguard assessments. The Vanguard data will be important in the stakeholders' work to finalize the protocol, and modify and finalize patient and clinician education materials.

At the end of year one and in Q1 of year 2 site recruitment will be completed, training and IRB approval of the final protocol will occur.

The first patient will be enrolled at the end of Q1 of Year 2, and enrollment will end during Q1 Year 4 with follow up of last patient completed by Q1, year 5.

For Vanguard 5 months after the contract, and complete it within 6 months Throughout the period of patient enrollment and follow up, we will work with our patient and other stakeholders to address implementation issues such as slow recruitment, incomplete patient retention, problems with training materials, low response to monthly surveys and other issues that arise. The patients will help identify and resolve barriers around these issues and help us modify processes as required.

In year 4, [name] will begin working with the stakeholder groups to finalize dissemination goals and specific strategies to facilitate widespread uptake of PARTICS (See Dissemination and Implementation).

Data cleaning and analysis will occur in Q2 4 of Year 5.

Interpretation of the results as well as manuscript preparation and final crafting of understandable patient messaging and other early dissemination activities will be finalized in Q3 and Q4 of year 5 with a final face to face stakeholders' meeting in Q3 or 4 of year 5.

A final report of the study will be completed in month 60.

### **III. Study Outcomes and Statistical Analysis**

#### **A. Patient-centeredness of PREPARE outcomes**

This study is designed to use real-world patient-reported outcomes (exacerbations, asthma control, quality of life, missed activities) that are of demonstrated importance to patients, providers, payers, and policy makers. Below we describe the patient-centeredness of our primary and major secondary outcomes.

#### **B. Primary Outcome**

Vanguard: We will be doing multiple assessments about the implementation and operationalization of the study processes. We will use descriptive statistics and qualitative analyses. Questionnaires administered to participants are included in the appendix.

Full study differences: We will be analyzing questionnaire data to address our hypotheses. There will be no assessments with regards to study processes as in the Vanguard phase.

Rate of asthma exacerbations per year is the primary outcome of this trial. It has been argued that exacerbations are the most important asthma outcome, because they constitute the greatest risk to patients, and are a cause of anxiety to patients and their families. All of our patient partners agreed that exacerbations have major impacts on their lives and would be

interested in using PARTICS if it would prevent or significantly reduce exacerbations. In addition to their effects on patients, exacerbations result in a great stress on health care providers (Lane 2006, Skrepnek 2004, Andersson 2003) and are of high importance to payers and health care policy makers. Exacerbations increase the risk of asthma mortality (Jorgensen 2003) and generate the greatest cost to the health care system (Reddel 2009, Lane 2006). Asthma exacerbations are recognized as a common clinical manifestation in patients with all levels of asthma severity (Pauwels 1997, O'Byrne 2001). National consensus guidelines have defined an asthma exacerbation as a worsening of asthma reported by the patient of a degree that requires treatment with corticosteroids (Revicki 1998).

The standardization of how we define asthma exacerbations was the focus of both an ERS/ATS Task Force (Reddell 2009) and a workshop sponsored by the NIH ([name] 2012).

Our primary outcome, the rate of asthma exacerbations per year, is defined as the number of exacerbations, emergency room visits, or hospitalizations requiring oral or parenteral corticosteroids, per patient per year. It will be captured by subject self-report via a monthly asthma exacerbations questionnaire (AEQ). Reports will be substantiated by verification in the EHR or direct patient interview. Multiple clinical trials demonstrate convergent validity with other measures of asthma-related health status (Busse 2011, Peters 2010, Lemanske 2010) and their responsiveness to intervention (O'Byrne 2005). We previously developed, tested, and used the AEQ as part of the BELT trial, in which we enrolled >1,000 AA patients. The AEQ is sensitive but not specific, meaning it overestimates the number of true exacerbations and therefore requires confirmation, but is not likely to miss exacerbations. Therefore, we will use the medical records or, if necessary, contact all patients whose form suggested an exacerbation to confirm. We will categorize these exacerbations as to whether they resulted in a hospitalization or emergency department visit. Using all sources of data available, an independent group of physicians (who are blinded about patient's randomized treatment) will adjudicate and classify all possible asthma exacerbation events to determine if an exacerbation is truly a primary endpoint event. All adjudications will be based on a document with pre-specified rules for adjudication.

## C. Secondary Outcomes

### 1. Asthma Control: Asthma Control Test (ACT) score

Asthma control represents the degree to which impairment (impact of asthma on patient's daily life) is minimized and the goals of therapy are met. The National Asthma Education and Prevention Program's Expert Panel Report 3 (NAEPP 2007), of which Drs. [name] and [name] were members or reviewers, emphasizes the importance of asthma control as a goal of therapy because of its relevance to patients and providers in the ongoing assessment of asthma. With the input of our stakeholders we will use the ACT (rather than the ACQ) for monthly outcome measures of asthma control. The Asthma Control Test (ACT) (described in D.III.8) measures asthma control—attainable only by patient report—and was developed to have low patient burden (Nathan 2004). Scores from the ACT allow providers to rapidly determine whether a patient's asthma is controlled or not (Nathan 2004). The ACT is self-reported and has been validated in multiple settings (office setting, mail, & by telephone) (D.III.8-Validation of Scales).

The ACT is easy to use, patient completed, and assesses the frequency of shortness of breath, use of rescue medications, the effect of asthma on daily functioning, and overall self-assessment of asthma control. The ACT has been evaluated in independent study population

samples and can be self-administered in person or at home (Schatz 2007a), by telephone (Schatz 2007b) and by mail (Schatz 2007c). The ACT has been recommended by the NAEPP and the NIH Asthma outcome workshop (NAEPP 2007, Cloutier 2012) because of the extensive validation data for these tools, using the widest range of criterion and construct measures, including demonstration of responsiveness to therapy and a minimal clinically important difference (MCID). The MCID is defined as the smallest difference in a given score of interest which patients perceive as beneficial and which would support a change in the patient's management (Jaeschke 1989). The MCID for the ACT has been defined as 3 for individuals over time and between populations (Schatz 2009) and cut-off values for uncontrolled asthma: ACT  $\leq$  19 (Nathan 2004), and "very poorly controlled" asthma: ACT  $\leq$  15 have been established. (Schatz 2006, Nathan 2004). Asthma APGAR will be used as a secondary assessment of control to see if the three questions with a shorter time reference and therefore less risk of recall bias can be used to replace the ACT. (Rank, MCP 2014).

## **2. Preference Based Quality of Life: Asthma Symptom Utility Index (ASUI)**

The ideal outcome measure for any comparative effectiveness analysis captures the risks and benefits for each of the interventions from the patient's point of view. The use of a preference-based instrument, the Asthma Symptom Utility Index (ASUI), captures this important information (Revicki 1998). The measure is entirely patient experience focused. To develop this measure, patients were asked to assign a relative value to different health states. The ASUI has two important features that highlight its importance to patients: 1) the ASUI captures the tradeoff of the positive and negative aspects of interventions from the patient's point of view, and 2) the ASUI measures the severity and impact of asthma symptoms. For asthma, the type and severity of asthma symptoms can differ between individuals or differ in a given individual over time. In addition, certain symptoms may be more troublesome than others to patients, and certain treatments might be more or less desirable. Whereas a patient with severe asthma might not appear to improve in terms of having significant symptom free days, s/he might improve in the severity and or frequency of the symptoms, something that is not captured by symptom-free day scales. The ASUI is probably the symptom scale most frequently used in asthma studies including large multicenter clinical trials (Boushey 2005). The ASUI's psychometric properties are well documented and support the reliability and construct validity of the instrument, including internal consistency reliability and test-retest reliability. The minimum clinically important difference has been determined as 0.09 points (Bime 2012).

## **3. Days Lost from Work or School or Usual activities**

As highlighted by our patient partners in our focus groups, days lost from work and school are a great concern for asthma patients. At the request of the patient partners, we have included this outcome measure. Days lost from work and school will be collected using a validated questionnaire developed and utilized as part of the National Health Interview Survey (NHIS 2014). If a patient does not work or go to school they are asked a question about days he/she was unable to carry out usual activities due to asthma. Our patient partners felt that this was a very important outcome that they would be interested in.

## **4. FeNO**

Fractional exhaled nitric oxide (FeNO): Exhaled nitric oxide gas will be measured during the study visit. Asthma is an inflammatory disease of the lung. The PREPARE trial relies on the fact that in many cases asthmatic inflammation is of the eosinophilic (or Type 2) form of inflammation.

Corticosteroids are particularly effective in targeting Type 2 inflammation. While inhaled corticosteroids (ICS) were initially thought to be a therapy for all asthmatics, studies now suggest that up to half of asthmatics may have non-type 2 inflammation and thus may be less responsive to ICS (Woodruff 2009). Thus, it is possible that PARTICS may be most beneficial for a particular group of patients – those with Type 2 mechanisms of inflammation.

## 5. Blood draw/Eosinophils

Peripheral blood eosinophils may identify asthmatics that are most responsive to Patient Activated Reliever-Triggered Inhaled CorticoSteroid (PARTICS). Eosinophil counts can be calculated by a complete blood count with differential. We will determine whether peripheral blood eosinophil count serves as an effect modifier of the relationship between treatment (PARTICS vs. usual care) and the study's primary outcome (number of asthma exacerbations per year). We will stratify participants based on a pre-specified peripheral blood eosinophil count threshold of 300/uL. This threshold is based on a frequently-used cutoff for 'eosinophil-high' status in the anti-eosinophil therapy literature (Giannetti 2016).

## D. Exploratory Outcomes

### 1. Asthma deteriorations:

Asthma deteriorations are defined as episodes of increased asthma symptoms for two or more days which resulted in patient determined increases in usual asthma medications without hospitalization, emergency department visit or prescription of oral steroids. In the previous mentioned BELT study (Wechsler 2015), we found that some patients chose not to seek medical care despite significant levels or length of increased symptoms due to transportation or financial barriers or health beliefs. However, these individuals did report increased use of the medications previously prescribed for their asthma. Evaluating both exacerbations and deteriorations may provide a more complete picture of the impact of the intervention on changes in asthma control and acute increases in symptoms.

### 2. The Asthma Medication Ratio (AMR)

This is a metric used by HEDIS to assess quality of asthma care in healthsystems. It is calculated as the rate of controller therapy refills over the controller therapy plus the rescue therapy refills over a period of one year. In a subset of enrolled patients, we will use the available pharmacy reported fill data from the patient's health care system plus the ICS fill data from Teva for the intervention group to calculate AMR in the enhanced usual care and intervention arms.

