## Protocol Summary

Asthma imposes a significant burden on the US population in terms of morbidity, costs to society, individual suffering, loss of productivity and mortality. African Americans (AA) and Hispanic/Latinos (H/L) bear a disproportionate share of that morbidity. Despite introduction of national guidelines for asthma treatment, the gap between these groups and whites has been stable or widening. The need for pragmatic research to address the continuing burden is widely recognized. Patients use asthma reliever inhalers to provide immediate relief of symptoms. Controller inhalers (inhaled corticosteroids (ICS)) are intended to be used regularly to prevent symptoms and attacks. Guidelines suggest that they be used daily, on a fixed basis, in all but the mildest asthma. However, adherence by patients and implementation of evidence-based guideline recommendations by clinicians has been poor. Gap analysis suggests that it is difficult to improve adherence to the current recommendations without complex and resource- intensive interventions.

Studies have examined symptom-activated use of ICS triggered by use of a reliever medication. We call this approach PARTICS – Patient Activated Reliever-Triggered Inhaled CorticoSteroid. Explanatory, non-real world studies suggest that PARTICS can produce up to 50% reductions in asthma attacks compared with usual care, while reducing ICS use by half or more. However, these studies have been performed in pre- selected populations, which represent less than 5% of patients with asthma. They have been done with repeated education and adherence checks in both the intervention and control arms.

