##### 5. Medication Data:

For patients randomized to the intervention group, the amount of QVAR use (estimated in total refills per period) due to PARTICS treatment will be reported by summary tables. Information on all other medication use will be available only in subset of patients for whom pharmacy fulfillment data is available from their health system. When available, the total number of dispensed inhalers for all of the patients' usual maintenance medications and usual rescue medications will be reported in summary tables.

No formal statistical tests are planned.

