## 7. Exploratory Analyses

In addition to the exploratory subgroup analyses mentioned above, we will also explore whether patient characteristics such as BMI, ICS/LABA use vs. ICS use, co-morbidity (such as history of heart disease, cancer, stroke, diabetes, chronic kidney disease, COPD/emphysema/chronic bronchitis, HIV/AIDS, and hypertension), and prior exacerbations (e.g., exacerbation within 12 months prior to randomization) affect the apparent effectiveness of PARTICS by examining the interaction of these factors with treatment. In addition, we will explore whether self-perceived discrimination affect outcomes regardless of treatment assignment.

The effect of provider adherence and patient adherence on the effectiveness of the PARTICS intervention will also be investigated. We will collect information from patients regarding their medication use and have added “non-invasive” ways to monitor what actually happens after they are randomized to either the enhanced usual care group or the intervention group. To this end, we will collect and incorporate the following into our descriptive information and into our exploratory analyses: 1) Information on the refills of the ICS in PARTICS “non-invasively” through the renewals at the pharmacy; 2) Information on PARTICS “adherence” by cross-referencing the ICS data above with patient monthly report of usage on their questionnaires and SABA pharmacy fulfillment data if available; 3) Information on PARTICS effects on other asthma medication use by comparing medication use between the intervention and non-intervention groups by examining monthly self-report and cross-referencing to pharmacy fulfillment data; 4) Measure of provider compliance with guidelines, by assessing whether providers adjust medications according to NAEPP guidelines. We will obtain this information “non-invasively” by examining EHR medication prescribing information at asthma related visits (none required by study). For each of these visits, we will refer to the patient’s self-reported asthma control score of the prior month (provided by the patient monthly questionnaire). We will examine medication prescribing at that visit from the EHR to assess the frequency with which providers stepped up, or stepped-down, care according to guideline recommendations (NAEPP, 2007); Patient adherence and provider adherence between the two treatment groups will be compared.

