The analyses on the exploratory outcomes will also be performed. The rate on asthma deteriorations will be reported by treatment groups. The composite endpoint of asthma deteriorations or exacerbations will be analyzed using the same Andersen-Gill version of the Cox proportional hazards model as used in the primary analysis. The Asthma APGAR data will be analyzed using the same mixed model approach as described above in the Asthma Control Test (ACT) score analyses.

Data on the Asthma Medication Ratio (AMR) during the follow-up months, the total health care utilization (i.e., total number of visits made to the enrolling sites, total number of ED visits, and total number of hospitalizations), and asthma related health care utilization (i.e., number of visits made to the enrolling sites, number of ED visits, and number of hospitalizations for which asthma is a first or second diagnosis) will be summarized. Differences between two randomized treatment groups on these variables will be compared using either t-test or Kruskal-Wallis test if full follow-up is available on everyone or Poisson or Negative Binomial regression models with time as an offset to account for differential duration of follow-up.

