## **D. Potential Benefits and Importance of the Knowledge to be Gained**

### **1. Benefits to Human Subjects and Others**

We believe there may be a potential benefit to those patients randomized to the PARTICS arm but this is still unknown. The potential benefit would be decreased numbers of exacerbations (asthma episodes that require oral steroid bursts or hospitalizations) and possibly decreased symptoms and reduced need for extra asthma medications. It is also possible that implementation of the Asthma IQ training for standardized provider educated care may improve rates of asthma control and this benefit could accrue to patients *in both arms* of the study.

Asthma has been resistant to various approaches to improve outcomes. Most approaches to date have focused in improving clinician implementation of current clinical guidelines and improving patient adherence with these treatment guidelines but when successful have been complex and difficult to widely disseminate. A few projects have worked at the community level to improve environmental conditions, but are also difficult to disseminate widely.

The approach studied in this project puts the patient in control of the level of additional use of ICS controller medications. The potential for benefit to society and individuals with asthma in general is very significant as the PARTICS represents a new approach to asthma therapy. Current asthma controller therapy follows a rigid, provider- prescribed approach. This study will examine the potential benefits of a patient controlled approach added to typical use of daily controller medications. Multiple studies and quality improvement projects have attempted to reduce asthma exacerbations, a theoretically ambulatory care-sensitive condition, with little long term improvement in outcomes. Any chance to determine a method to close this gap in care and learn how better to treat these subjects in clinical practice presents a clear benefit to African American and Hispanic/Latino adults with asthma.

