Our proposed study seeks to inform a key health decision for people with asthma and clinicians who treat it-- should asthma patients use, and providers prescribe, a controller medication to be used each time a reliever is used in order to reduce asthma exacerbations? The PREPARE trial can help with that decision by assessing the ability of PARTICS to reduce exacerbation occurrences, reduce days lost from school or work, and reduce the consumption of ICS – all outcomes of high importance to patients.

This health decision is particularly pertinent among AAs and H/Ls, who bear a disproportionate burden of asthma morbidity and are less likely to receive, choose, or be able to comply with guideline-driven care. If the study shows that the PARTICS approach reduces exacerbations and/or improves other outcomes important to patients, then this approach can easily be adopted by patients and their providers in the context of current care since it is intuitive and

takes advantage of current patient-driven patterns of reliever inhaler use.

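### The planned Asthma Medication Ratio counts study ICS fills that only one arm can have, so without a companion own-fill ratio a between-arm difference cannot by itself show a difference in own controller use or care quality

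*Combined protocol and SAP*

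**What the plan says.** Section III.D.2 introduces the AMR as a health-system quality-of-care metric and defines it as "the rate of controller therapy refills over the controller therapy plus the rescue therapy refills over a period of one year". It is to be computed in a subset of patients, from pharmacy fill data held by their health system, "plus the ICS fill data from Teva for the intervention group to calculate AMR in the enhanced usual care and intervention arms". Usual-care patients receive no study ICS, so this second source of fills exists in one arm only.

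Section III.E.7 lists the AMR among the variables to be summarised and states: "Differences between two randomized treatment groups on these variables will be compared using either t-test or Kruskal-Wallis test". It gives a count regression as the alternative where follow-up differs.

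The plan does not say outright that study ICS goes into the controller count, but its own vocabulary points that way. The Protocol Summary says: "Controller inhalers (inhaled corticosteroids (ICS)) are intended to be used regularly to prevent symptoms and attacks". Section VII.D.1 describes the strategy as "additional use of ICS controller medications" under the patient's control, and the question under study as whether to use "a controller medication to be used each time a reliever is used".

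Related material appears in three places:
- Section III.D.5 tabulates study-drug refills and, separately, dispensed inhalers: "usual maintenance medications and usual rescue medications will be reported in summary tables". No formal tests are planned there.
- Section III.E.7, item 3, examines "PARTICS effects on other asthma medication use by comparing medication use between the intervention and non-intervention groups".
- Section III.E.7, item 4, with section II.C.8, assesses clinicians' adherence to guidelines, including controller prescribing, step-up and step-down.

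None of these defines an AMR from patients' own fills or says how a between-arm AMR difference will be read.

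**The concern.** A ratio described as a care-quality metric would ordinarily be read as the balance between a patient's controller and reliever dispensing. Here the intervention supplies one of the ingredients directly. Two patients with identical own fills receive different ratios because of their arm. In the other direction, a fall in own controller fills can be hidden by study fills.

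The ratio also behaves differently by arm. Under the puff-for-puff instruction (section VII.B.2), rescue use triggers study ICS use. In usual care an extra rescue fill only lowers the AMR, whereas in the intervention arm it can also add study fills to the numerator.

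What is at stake is limited to how one exploratory comparison in a subset is described.

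**Working it through.** The documents state no AMR value, effect size or power, so there is no figure to reproduce. The check is arithmetic on the section III.D.2 definition.

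**Notation, fills per year.** C is own controller fills, R is own rescue fills and T is study ICS fills from Teva, counted as controller.

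- Own-fill AMR = C/(C+R). In usual care this is also the planned AMR.
- Planned (inclusive) AMR in the intervention arm = (C+T)/(C+T+R).
- Difference with identical own fills = T·R / [(C+R)(C+T+R)], which is positive whenever T>0 and R>0.

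The direction is therefore algebraic. The size depends on fill counts that the documents do not give for this trial.

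**Inputs for the illustration.** C = 3 borrows the background figure in section I.B.4 (about three months of prescriptions filled in a year); it is not a trial estimate. R and T are assumptions.

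**Identical own fills, C = 3, R = 4, T = 2.**
- Usual care: 3/7 = 0.429.
- Intervention: (3+2)/(3+2+4) = 5/9 = 0.556.
- Difference: 0.127, with no difference in own fills.

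**Range.** With C of 3, 6 or 12, R of 3, 6 or 12, and T of 1, 2, 4 or 6:
- Smallest difference (C=12, R=3, T=1): 13/16 − 12/15 = 0.8125 − 0.8000 = 0.0125.
- Largest difference (C=3, R=6, T=6): 9/15 − 3/9 = 0.600 − 0.333 = 0.267.

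**Replacement, R = 4.** Suppose t study fills replace t own controller fills, starting from C = 3:

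| t | Own controller fills | Study fills | Inclusive AMR | Own-fill AMR |
|---|---|---|---|---|
| 0 | 3 | 0 | 3/7 = 0.429 | 3/7 = 0.429 |
| 1 | 2 | 1 | 3/7 = 0.429 | 2/6 = 0.333 |
| 2 | 1 | 2 | 3/7 = 0.429 | 1/5 = 0.200 |

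The inclusive ratio does not move while the own-fill ratio falls by more than half. This is arithmetic, not a forecast. Section II.C.11 says both arms stay on their existing controllers. Sections VII.B.2 and VII.C.3 anticipate lower ICS dose or use over time, but dose and use are not fill counts.

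**After the change.** With an own-fill AMR in both arms, identical own fills give a difference of exactly zero.

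**The case against.** The strongest reply is that the plan never draws the inference at issue. No section says that an AMR difference will be taken as better care or as more use of patients' own controllers; the description of the metric may only say where it comes from. In a comparison of strategies by randomized arm, counting everything dispensed under each strategy is defensible, and the gap above is then simply the extra ICS that the strategy supplies. This stands: including study ICS is not an error. What remains is that the plan gives no interpretation for a ratio it introduces as a quality metric.

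A second reply is that the components are already separated. Section III.D.5 and section III.E.7, item 3, cover own medication use, and item 4 with section II.C.8 measures guideline adherence directly. This also largely stands. A reader might infer that care quality in this trial rests on the AMR; the documents do not support that. They do not, however, supply the own-fill ratio.

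A third reply concerns the remedy. It is tempting to treat the own-fill AMR as the true quality measure. The documents do not support this either. Section VII.B.2 expects clinicians to lower ICS dose as control improves, section VII.C.3 expects ICS use to fall, and section II.C.8 counts step-down after sustained control as following guidelines. A lower own-fill AMR may therefore reflect step-down and not worse care.

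A reader might also infer real doubt about whether the first study inhaler counts, since the definition speaks of refills. That doubt is weak. The operative sentence uses Teva fill data, and section VII.B.1 has the study inhaler filled by the central pharmacy, so the natural reading counts every Teva fill.

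**Conclusion.** The point holds as a cheap improvement of minor severity. As planned, the between-arm AMR comparison mixes drug supplied by the strategy with patients' own controller dispensing. By itself it cannot show a difference in own controller use or care quality. The direction of the effect at identical own fills follows from the definition, provided study ICS is counted as controller, which is the natural reading.

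The sizes, such as 0.43 against 0.56, rest on assumed fill counts and are not estimates of a bias in this trial. The actual net difference is unknown and need not be positive. The AMR is exploratory and computed in a subset, and no primary or secondary result is affected.

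**What to change.** In section III.D.2, label the planned AMR as the ICS share dispensed under each strategy, and state that all Teva fills count as controller.

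In section III.E.7, report beside it an AMR from health-system pharmacy fills only, in both arms, with the number of patients per arm for whom it is undefined (0/0, no health-system fills). Use the own-fill version only to describe the balance of own controller to rescue fills. State that neither version alone is read as care quality, and refer such statements to the guideline-adherence measures in section III.E.7, item 4, and section II.C.8.

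The cost is a few sentences and one extra exploratory table row; the fill data are already planned in sections III.D.2 and III.D.5. The downside is that the own-fill version ignores study ICS that was actually dispensed, so the two rows must be read together.
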